2.1.3 Assessment windows, baseline and post baseline definitions, missing data handling

2.1.3.1 Study day

The study day for all post-treatment assessments (e.g. efficacy and safety) is calculated as the difference between the date of the event (visit date, onset date of an event, assessment date, etc.) and the date of first administration of non-zero dose of study treatment plus one day. The first day of study treatment is therefore Study Day 1.

The study day for all pre-treatment assessments is calculated as the difference between the date of the event and the date of first administration of non-zero dose of study treatment. The last day prior to PDR001 administration is therefore Study Day -1. For the particular case of pretreatment assessments performed on the day of first administration, the study day is set to Day

Unless specified otherwise, the study day is displayed in the data listings.

2.1.3.2 Baseline

Baseline is the result of an investigation describing the "true" state of the subject before start of study treatment administration.

Baseline (e.g. for laboratory parameters) is considered as the last non-missing assessment or value before start of the first treatment, unless otherwise stated under the related assessment.

Baseline could be within 21 days (or 28 days for radiological evaluations) before first treatment administration or on the same day as first treatment administration if specified pre-dose (e.g., ECG).

If time is recorded for the first treatment dose and for a specific assessment performed the day of first dose, this assessment is considered as baseline only if it is actually performed before the first dose, as checked using both times.

If time is not recorded, a specific assessment performed the day of first dose administration is considered as baseline if, according to protocol, it should be performed before the first dose.

In rare cases where multiple measurements meet the baseline definition, with no further flag or label that can identify the chronological order, then the following rule should be applied: If values are from central and local laboratories, the value from central assessment should be considered as baseline. If multiple values are from the same laboratory (local or central) or collected for ECGs or vital signs, then the last value should be considered as baseline.

Patients with no data on a particular parameter before the first treatment administration will have a missing baseline for this parameter.

For ECG evaluations three serial 12-lead ECGs will be obtained on Cycle 1 Day 1 for each patient, prior to the first administration of PDR001 (C1D1). The average of the triplicate ECG measurements will serve as the patient's baseline value for post-dose comparisons.

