### 5.3 Exclusion criteria

Patients eligible for this study must not meet **any** of the following criteria:

1. Presence of symptomatic central nervous system (CNS) metastases, or CNS metastases that require local CNS-directed therapy (such as radiotherapy or surgery), or increasing doses of corticosteroids within the prior 2 weeks.
2. History of severe hypersensitivity reactions to other mAbs
3. Patient having out of range laboratory values defined as:

- Creatinine clearance (calculated using Cockcroft-Gault formula, or measured) < 40 mL/min
  - Total bilirubin > 1.5 x ULN, except for patients with Gilbert's syndrome who are excluded if total bilirubin > 3.0 x ULN or direct bilirubin > 1.5 x ULN
  - Alanine aminotransferase (ALT) > 3 x ULN, except for patients that have tumor involvement of the liver, who are excluded if ALT > 5 x ULN
  - Aspartate aminotransferase (AST) > 3 x ULN, except for patients that have tumor involvement of the liver, who are excluded if AST > 5 x ULN
  - Absolute neutrophil count <  $1.0 \times 10^9/L$
  - Platelet count <  $75 \times 10^9/L$
  - Hemoglobin (Hgb) < 8 g/dL
  - Potassium, magnesium, calcium or phosphate abnormality > Common Terminology Criteria for Adverse Events (CTCAE) grade 2
4. Impaired cardiac function or clinically significant cardiac disease, including any of the following:
    - Clinically significant and/or uncontrolled heart disease such as congestive heart failure requiring treatment (NYHA grade  $\geq 2$ ), uncontrolled hypertension or clinically significant arrhythmia
    - QTcF > 470 msec on screening ECG or congenital long QT syndrome
    - Acute myocardial infarction or unstable angina pectoris < 3 months prior to study entry
  5. Subjects with active, known or suspected autoimmune disease. Subjects with vitiligo, type I diabetes mellitus, residual hypothyroidism due to autoimmune condition only requiring hormone replacement, psoriasis not requiring systemic treatment, or conditions not expected to recur in the absence of an external trigger are permitted to enroll.
  6. History of drug-induced pneumonitis or current pneumonitis.
  7. Active infection requiring systemic antibiotic therapy.
  8. Human Immunodeficiency Virus (HIV) infection.
  9. Active HBV or HCV infection.

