### 7.2.2.6 Cardiac assessments

#### 7.2.2.6.1 Electrocardiogram (ECG)

A standard 12 lead ECG will be performed as per the assessment schedule in Table 7-1 and Table 7-5. Blood samples scheduled at the same time point should be taken after the ECGs are completed. For the Screening only one ECG per visit is required. Unscheduled visits can be either one ECG or in triplicate based on investigator's choice on which is most appropriate.

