3.5.3.3 Data analysis

On analyzing laboratory, data from all sources (central and local laboratories (as applicable)) will be combined. The summaries will include all assessments available for the lab parameter collected no later than 30 days after the last study treatment administration date (see Section 2.1.3.3).

The following listing will be produced for the laboratory data:

• Listing of all laboratory data with values flagged to show the corresponding CTCAE 4.03 grades if applicable and the classifications relative to the laboratory normal ranges

The following summaries will be generated separately for hematology and biochemistry tests:

For laboratory tests where grades are defined by CTCAE 4.03:

- Worst post-baseline CTCAE grade (regardless of the baseline status). Each patient will be counted only once for the worst grade observed post-baseline.
- Shift tables using CTCAE 4.03 grades to compare baseline to the worst on-treatment value

For laboratory tests where grades are not defined by CTCAE 4.03:

• Shift tables using the low/normal/high/ (low and high)

Table 3-3 lists all laboratory parameters for which CTCAE grades are defined.

Table 3-3 Laboratory parameters to be listed and presented in grade shift tables based on CTC grade

Hematology and coagulation		Biochemistry	
White Blood Cells (WBC)	$\uparrow\downarrow$	Albumin	\downarrow
Hemoglobin	\downarrow	Alkaline phosphatase	↑
Platelets counts	\downarrow	ALT (SGPT)	↑
Absolute Neutrophils	\downarrow	AST (SGOT)	↑
Absolute Lymphocytes	$\uparrow\downarrow$	Glucose	$\uparrow\downarrow$

Novartis	Confidential			Page 40
SAP final CSR	24-Jul-2020 (11:48)			CPDR001X2101
	activated partial thromboplastin time (APTT)	1	Calcium	$\uparrow\downarrow$
	International normalized ratio (INR)	↑	Total Bilirubin	↑
			Creatinine	↑
			Potassium	$\uparrow\downarrow$
			Magnesium	$\uparrow\downarrow$
			Sodium	$\uparrow\downarrow$

[↑] Indicates that CTC grade increases as the parameter increases, these parameters are to be included in the summary of maximum post-baseline lab parameters

Table 3-4 lists all laboratory parameters to be listed based on local laboratory normal ranges.

Table 3-4 Laboratory parameters to be listed based on local laboratory normal ranges

_	
Hematology and coagulation	Biochemistry
Absolute eosinophils	Urea
Absolute basophils	Blood urea nitrogen (BUN)
Absolute monocytes	Direct bilirubin
	Indirect bilirubin
	Bicarbonate
	Chloride
	T4
	TSH
	IL-6
	IFN-γ

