3.5.3.5 Biochemistry

Biochemistry includes the following parameters: urea or blood urea nitrogen (BUN), creatinine, sodium, potassium, calcium, albumin, direct and total bilirubin, alkaline phosphatase, AST,

[↓] Indicates that CTC grade increases as the parameter decreases, these parameters are to be included in the summary of minimum post-baseline lab parameters

ALT, glucose, magnesium, chloride, bicarbonate,, inorganic phosphate, urinalysis, thyroid function (T4, TSH) and cytokines (IL-6, IFN-γ).

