3.5.6 Electrocardiograms

The average of the ECG parameters at that assessment should be used in the analyses.

A listing of all ECG assessments will be produced by treatment and notable values will be flagged. In the listing, the assessments collected during the post-treatment period will be flagged.

The number and percentage of subjects with notable ECG values will be presented by treatment (see Table 3-6).

Table 3-6 Notable ECG values

ECG Parameter	Abnormal values
QT, QTcF and QTcB	New value of > 450 and ≤ 480 ms
	New value of > 480 and ≤ 500 ms
	New value of > 500 ms
	Increase from baseline of > 30 ms to ≤ 60 ms
	Increase from baseline of > 60 ms

Novartis	Confidential	Page 42
SAP final CSR	24-Jul-2020 (11:48)	CPDR001X2101
HR	Decrease from baseline >2 beats/min	25% and to a HR < 50
	Increase from baseline >25 beats/min	5% and to a HR >100
PR	Increase from baseline >25	5% and to a value >200 ms
	New value of > 200 ms	
QRS	Increase from baseline >25	5% and to a value >120 ms
	New values of QRS > 120	ms

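### SAP safety rules do not fully match Amendment 8: ECG baseline is not clearly defined for patients without a Cycle 1 Day 1 ECG, and inorganic phosphate is missing from both laboratory parameter tables

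*SAP*

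**What the plan says.** **ECG baseline.** SAP 2.1.3.2 gives a general rule, under which baseline "is considered as the last non-missing assessment or value before start of the first treatment, unless otherwise stated under the related assessment". The same section then has a paragraph for ECGs alone: "three serial 12-lead ECGs will be obtained on Cycle 1 Day 1 for each patient", before the first PDR001 dose. "The average of the triplicate ECG measurements will serve as" the baseline for post-dose comparisons. That baseline feeds the change categories in SAP Table 3-6 for QT/QTcF/QTcB, heart rate, PR and QRS, for example "Increase from baseline of > 60 ms".

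SAP Section 1 says this version follows Protocol Amendment 8. There, Table 7-1 schedules an ECG at screening and afterwards only when clinically indicated, and Table 7-5 has just a screening row and an unscheduled row. Protocol 7.2.2.6.1 adds: "For the Screening only one ECG per visit is required". Protocol Table 6-4 identifies the baseline ECG as the one or ones taken at screening.

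**Phosphate.** Protocol Table 7-4 includes inorganic phosphate in the chemistry panel. Exclusion criterion 3 (protocol 5.3) applies a CTCAE grade to it: "Potassium, magnesium, calcium or phosphate abnormality > Common Terminology Criteria for Adverse Events (CTCAE) grade 2". SAP 3.5.3.5 counts it as biochemistry, in a list that runs "inorganic phosphate, urinalysis, thyroid function (T4, TSH" and so on. SAP 3.5.3.3 says that "Table 3-3 lists all laboratory parameters for which CTCAE grades are defined", and Table 3-4 covers the parameters classified by local normal range. Phosphate is in neither. SAP 3.5.3.3 and protocol 10.5.3.3 both call for shift tables for biochemistry tests, and the SAP adds worst-grade tables.

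**The concern.** Changes in laboratory parameters and ECGs are part of the secondary safety endpoint in protocol Table 3-1 and SAP Table 1-1, so the rules behind those outputs should match the data collected.

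The ECG paragraph describes a visit procedure that Amendment 8 no longer contains. A patient who started under the current schedule has a screening ECG but no C1D1 triplicate. One programmer could set that patient's baseline to missing because the ECG rule is not met. Another could fall back on the screening value. The two would produce different change-from-baseline counts from the same data.

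For phosphate, the SAP's text and its tables disagree. If the tables drive the programming, a collected electrolyte drops out of the worst-grade and shift summaries, while potassium, magnesium, calcium and sodium remain in them.

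**Working it through.** **1. Which ECG baseline rule governs.** The general rule gives way wherever a specific assessment states something else. The ECG paragraph does state something else: a triplicate, on C1D1, averaged, for each patient. It says nothing about a patient with no triplicate. It also sits awkwardly with the tie rule in the same section. When several ECG values qualify and their order cannot be established, that rule takes the last one instead of averaging.

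**2. How many patients could lack a C1D1 ECG.** The amendment history places the removal of the C1D1 ECG in Amendment 06, dated 27-Jul-2017. The nearest patient count in the protocol is at 29-Jun-2017 (study status, Amendment 06). The final count is in the Amendment 08 study status.

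| Part or group | Treated by 29-Jun-2017 | Treated in total | Started later |
|---|---|---|---|
| Dose escalation | 58 | 58 | 0 |
| NSCLC | 114 | 118 | 4 |
| Melanoma | 61 | 61 | 0 |
| TNBC | 40 | 40 | 0 |
| Anaplastic thyroid | 13 | 42 | 29 |
| All | 286 | 319 | 33 |

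- Share of all treated patients: 33/319 = 10.3%.
- Anaplastic thyroid: 29/42 = 69.0%.
- NSCLC: 4/118 = 3.4%.
- Started while the schedule still had a C1D1 ECG: at least 286/319 = 89.7%.

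The 33 is an upper bound. The count date is about four weeks before the amendment date, and the amendment needed ethics approval before use, so some of the 33 may still have had C1D1 ECGs.

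**3. How many results are affected.** A change-from-baseline category needs a post-baseline ECG as well as a baseline. Under Amendment 8 an on-treatment ECG is taken only if clinically indicated. The affected number is therefore the subset of the 33 with no C1D1 triplicate and at least one on-treatment ECG. The documents do not give it.

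**4. Phosphate.** Each chemistry test in protocol Table 7-4 was compared with the two SAP tables.

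- In Table 3-3: albumin, alkaline phosphatase, ALT, AST, calcium, sodium, potassium, creatinine, glucose, magnesium, total bilirubin.
- In Table 3-4: bicarbonate, chloride, direct and indirect bilirubin, urea or BUN.
- In neither: inorganic phosphate, the only chemistry test left over.

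The SAP gives no reason for leaving it out.

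**The case against.** **ECG.** The best reply is that the general rule fills the gap. SAP 2.1.3.2 reserves a missing baseline for patients with no pre-treatment data on a parameter, and the schedule gives every patient a screening ECG. If no triplicate was taken, its average does not exist, and the last pre-dose value can stand in. That reading is reasonable and agrees with protocol Table 6-4. It does not settle the matter, because the ECG paragraph is specific, is worded for each patient and names no alternative. What stands is that baseline is unclear for these patients, not that it is certainly missing.

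A reader might infer that QTc change goes unevaluated in most ATC patients because of this sentence. The documents do not support that. The protocol deliberately moved to clinically indicated ECGs, and a patient without one has no post-baseline value under any baseline definition. Changing the SAP would not alter that.

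**Phosphate.** The reply is that SAP 3.5.3.1 grades laboratory values by CTCAE, or by normal range where no grade exists, and that SAP 3.5.3.3 orders summaries for biochemistry, which 3.5.3.5 says includes phosphate. On that text phosphate would be summarised, and the tables are simply incomplete. This is fair, and it makes the defect an internal conflict. But Table 3-3 claims to be the full list of graded parameters, so the conflict needs resolving.

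A reader might also infer that phosphate abnormalities would be seen only in a listing. That goes too far: protocol 8.1.1 and 8.1.2.1 require abnormalities that are clinically significant, cause symptoms, or need therapy or a treatment change to be recorded as adverse events, and these are tabulated.

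Table 3-3 crosses a page break in the public copy. A lost row cannot be fully excluded, although neither table shows a gap.

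**Conclusion.** Both mismatches stand in the current text.

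- **ECG:** the SAP's ECG-specific baseline rests on a measurement that Amendment 8 does not schedule, and it has no fallback. It remains usable for the roughly 90% of patients who started under the earlier schedule, assuming their triplicates were taken. Baseline is unclear for at most 33 of 319 patients, concentrated in the separately reported anaplastic thyroid group. The 33 bounds the patients who may lack a C1D1 ECG and is not a count of lost QTc evaluations. The number of Table 3-6 entries affected is unknown and may be small, though those ECGs would have been taken for a clinical reason.
- **Phosphate:** its absence from Tables 3-3 and 3-4 conflicts with SAP 3.5.3.3 and 3.5.3.5 and with protocol 10.5.3.3. If the tables are followed, abnormalities that do not qualify as adverse events appear only in the laboratory listing, for all treatment groups.

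The effect is confined to secondary safety summaries. The primary endpoint and sample size are not touched.

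**What to change.** 1. In SAP 2.1.3.2, replace the ECG paragraph with: *ECG baseline = mean of the C1D1 pre-dose triplicate if taken, otherwise the last ECG (or mean of replicates) before first dose.* Report, by treatment group, how many patients use each source.
2. Add inorganic phosphate to SAP Table 3-3. Take the grading direction from the sponsor's CTC grading criteria cited in SAP 3.5.3.1. The protocol and SAP do not state a direction, and exclusion criterion 3 refers only to an abnormality. First check the signed SAP to confirm that the row really is absent.

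The cost is one sentence, one small count table and one table row, using data the protocol already collects. SAP Section 1 gives the route: an amendment before database lock or an addendum after it.

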2.1.3.3 On-treatment assessment/event and observation periods

The overall observation period is divided into three mutually exclusive segments:

- 1. pre-treatment period: from day of patient's informed consent to the day before first dose of study treatment
- 2. on-treatment period: from day of first dose of study treatment to 30 days after last dose of study treatment
- 3. post-treatment period: starting at day 31 after last dose of study medication.

If dates are incomplete in a way that clear assignment to pre-, on-, post-treatment period cannot be made, then the respective data will be assigned to the on-treatment period.

Safety summaries (tables, figures) include only data from the on-treatment period with the exception of baseline data which will also be summarized where appropriate (e.g. change from baseline summaries). Following last administration of PDR001, adverse events (including serious adverse events), and new antineoplastic therapies are collected for a period of 150 days. Following start of new antineoplastic therapy, only study treatment related adverse events are collected. Select summaries of related adverse events will be produced for the combined ontreatment and post-treatment periods (Section 3.5.2.2).

2.1.3.4 Cycle day and duration definition

A treatment cycle is defined as 28 days for the Q2W and Q4W regimens and 21 days for the Q3W regimen, for the purposes of scheduling procedures and evaluations.

Several visits are scheduled for each cycle [CPDR001X2101 Amendment 8 Table 7-1]. For all visits, there is a \pm 7 days window on assessments. Laboratory assessments that are completed within 3 days prior to C1D1 do not need to be repeated on C1D1.

The respective cycle number and day within cycle will be re-derived according to the following rules:

- C1D1 coincide with the start date of treatment.
- All pre-treatment assessments are displayed as Cycle 0 with a negative day (e.g., Day -1 is the day before the patient started treatment), or Cycle 1 Day 1 for assessment performed pre-dose on the day of the first administration of study treatment.
- Day 1 of a cycle corresponds to the day reported by investigator on the start of cycle.
- For all cycles but the last, the end date of a cycle is defined as the day before Day 1 of the following cycle as recorded.
- In the situation where a patient received the whole treatment cycle as planned (e.g., Cycle 1 for 4 weeks) but had an additional rest period (e.g., 1 week) in order to recover from AEs

before next cycle start, duration of cycle is then longer than originally planned (e.g., 5 weeks).

- The end date of the last cycle is when treatment administration is permanently discontinued at the latest of the following days:
 - o Date of last administration + 13 days for Q2W schedule;
 - Date of last administration + 20 days for Q3W schedule;
 - o Date of last administration + 27 days for Q4W schedule.
- All post-cycle assessments are displayed as follow-up and with, by analogy, Day 1 representing the first day after the end of the last cycle.
- The duration (in days) of a cycle is defined as: cycle end date cycle start date + 1. Cycle number and day within cycle are computed to be displayed in listings only.

2.1.3.5 Windows for analysis

Windows to be used for summaries of PK concentrations by scheduled time point are described in [CPDR001X2101 Amendment 8 Section 7.2.3], however, if outside the time window, these will not be excluded unless flagged by the CP expert – a comment would then be provided. Unless otherwise specified, when more than one assessment is available for a visit, all assessments will be listed under the visit while only the assessment closest to the planned day for the visit will used for summaries and analyses.

2.2 Imputation rule of partial or missing dates/data

Imputation rule of partial or missing dates

As a general rule, when a date is recorded as a partial date, the missing day is imputed to the 15th of the month (e.g., DEC2007 imputed to 15DEC2007), and if the day and month are both missing then to July 1st of that year (e.g., 2007 imputed to 01JUL2007). Such imputed data are flagged in the listings.

Imputation rules for AEs, medical history and concomitant medications partial or missing dates are defined in Section 4.1.1.

In order to be conservative, these rules tend to maximize the duration of AEs under treatment and are equivalent to the rule above otherwise.

For other partial dates, the general STL standard imputation rules are used.

For computation of time intervals (e.g. elapse time between initial diagnosis to first recurrence/relapse), if the imputation rule leads to a negative value, time interval should be set to missing.

Handling of missing values/censoring/discontinuation

Continuing events (e.g. AEs) will be summarized using the data cut-off date as the date of completion, with an indication within listings that the event is continuing. For patients who discontinue the study with ongoing events, the discontinuation date is used as the completion date of the event with the appropriate censoring.

The reasons for discontinuation from study will be listed, along with dates of first and last study treatment, and date of discontinuation for each patient.

Other missing data will simply be noted as missing on appropriate tables/listings.

2.3 **Analysis sets**

A patient must have given informed consent to participate in the study before being included in any analysis set.

Patients will be excluded from the analysis sets based on the protocol deviations and specific non-protocol deviations entered in the database. All protocol deviations and non-protocol deviations leading to exclusion from specific analysis set will be identified before database lock.

See Table 2-1 for non-protocol deviation leading to exclusion from analysis set definitions, and Table 2-2 for protocol deviation leading to exclusion from analysis set definitions.

All protocol deviations will be listed by treatment.

Patients who sign an informed consent but fail to be started on treatment for any reason will be considered a screen failure. The reasons for not being started on treatment will be entered on the Screening Log eCRF, and each patient's demographic information will be recorded on the Demography eCRF. For these patients, the eCRF data collected will not be included in analyses, but will be reported in the CSR as separate listings.

The following analysis sets are defined for the analysis of the study data.

